8.10 Other Aspects

Not applicable.

9 PROTECTION OF HUMAN SUBJECTS

9.1 Ethical Considerations

The procedures set out in this study protocol are designed to ensure that Recordati and investigator abide by the principles of the International Society for Pharmacoepidemiology GPP guidelines (*Ispe 2008*). The study will also be carried out in compliance with local legal requirements MR-004.

9.2 Informed Consent

Informed consent is not required for this study, because this study is a secondary data collection study using anonymised patient data. The authorisation for getting access to the medical data of the patients must also be ensured, through the existence of a signed general consent, or requesting a signed NOL, or fulfilling the conditions of a tacit approval or no written document stating they refused any participation to scientific research.

9.3 Protocol Approval and Amendment

Before the start of the study, the French health data hub will be notified with the study protocol and/or other relevant documents, in accordance with local legal requirements.

Final v2.0 55 of 63 18 April 2023

To alter the protocol, amendments must be sent to Competent Authority as notification prior to implementation.

Administrative changes (not affecting patient risk) may be made without the need for a formal amendment. All amendments will be distributed to all protocol recipients, with appropriate instructions.

9.4 Confidentiality

All study findings and documents will be regarded as confidential. The investigator and members of his/her research team must not disclose such information without prior written approval from Recordati.

The anonymity of participating patients must be maintained. Investigators shall ensure that personal identifiers will be removed from any study files that are accessible to non-study personnel in accordance with applicable laws and regulations. Patients will be identified on eCRFs, and other documents submitted to Parexel by their patient number, initials and/or birth date (if allowed), not by name. Documents not to be submitted to Parexel that identify the patient must be maintained in confidence by the investigator.

9.5 Duration of the Study

The study duration will be approximately up to 3 years. It will be retrospective follow-up period at every 12 weeks until the earlier of loss to follow-up (LTF), death, or the end of the retrospective follow-up period or treatment discontinuation.

10 MANAGEMENT AND REPORTING OF ADVERSE EVENTS/ADVERSE DRUG REACTIONS

Being retrospective chart review, it does not require active reporting of AEs/ADRs to regulatory authorities.

Final v2.0 56 of 63 18 April 2023

10.1 Definitions

Adverse events (AEs)

An AE is any untoward medical occurrence in a patient or clinical study participant administered a pharmaceutical product, whether or not considered related to the product. An AE can therefore be any unfavourable and unintended sign (including an abnormal laboratory finding, for example), symptom, or disease (new or exacerbated) temporally associated with the use of a product.

Treatment-emergent adverse events (TEAEs)

Any AE with an onset date on or after the study drug start date and no later than 30 days after last dose of study drug, or any worsening of any AE on or after the study drug start date.

Serious adverse events (SAEs)

An SAE is any AE that:

- Results in death.
- Is life-threatening. (Note: The term 'life-threatening' in the definition of 'serious' refers to an event in which the subject was at risk of death at the time of the event; it does not refer to an event that hypothetically might have caused death if it were more severe).
- Requires inpatient hospitalization or prolongation of existing hospitalization.
- Results in persistent or significant disability/incapacity.
- Is a congenital anomaly/birth defect.

• Is an important medical event. Important medical events that may not result in death, be life-threatening, or require hospitalization may be considered an SAE when, based upon appropriate medical judgment, they may jeopardize the patient and may require medical or surgical intervention to prevent one of the outcomes listed in this definition.

Adverse drug reaction (ADR)

An ADR is defined as a response to a medicinal product which is noxious and unintended. Response in this context means that a causal relationship between a medicinal product and an AE is at least a reasonable possibility, i.e., the relationship cannot be ruled out.

10.1.1 Categorisation of Adverse events

10.1.1.1 Severity Assessment

All AEs will be classified using the current version of the Common Terminology Criteria for Adverse Events (CTCAE) version 5.0, developed, and maintained by the Cancer Therapy Evaluation Program at the National Cancer Institute.

- **Grade 1**: Mild: asymptomatic or mild symptoms; clinical or diagnostic observations only; intervention not indicated; The AE is easily tolerated and does not interfere with daily activities.
- **Grade 2**: Moderate: minimal, local, or non-invasive intervention indicated; The AE interferes with daily activities, but the subject is still able to function.
- **Grade 3**. Severe: not immediately life-threatening; hospitalization or prolongation of hospitalization indicated; disabling; The AE is incapacitating and requires medical intervention. Every effort will be made to obtain an adequate evaluation of the severity.
- **Grade 4**. Life threatening: consequences; urgent or emergent intervention needed.
- **Grade 5**. Death related to or due to AE.

Final v2.0 58 of 63 18 April 2023

10.1.1.2 Causality Assessment

The following definitions of relationship to the study drug should be used to characterise the suspected causality of each AE, based on the investigator's consideration of all available information about the AE, including temporal relationship to drug administration, recognised association with drug product/class, pharmacological plausibility, and alternative aetiology (e.g., underlying illness, concurrent conditions, concomitant treatments):

- **Related** An AE that follows a reasonable possibility of a causal relationship to study drug i.e., reasonable temporal sequence from administration of a drug (including the course after withdrawal of the drug), or for which possible involvement of the drug cannot be ruled out, although factors other than the drug, such as underlying diseases, complications, concomitant drugs, and concurrent treatments, may also be responsible
- **Not Related** An AE that does not follow a reasonable possibility of a causal relationship to the study drug i.e., no reasonable temporal sequence from administration of a drug and/or that can reasonably be explained by other factors, such as underlying diseases, complications, concomitant drugs, and concurrent treatments.

10.2 Collection and Reporting of Adverse Events/Adverse Reactions

This study uses data from electronic and paper healthcare records. Consistent with regulatory requirements for a non-interventional study based on secondary use of data (EU Good Pharmacovigilance Practices VI.C.1.2.1), no reporting of AEs is required. It is assumed that any AEs identified in existing healthcare records have already been reported at the time it occurred in the past, therefore, no additional AE/SAE reporting will be made to regulatory authorities to avoid duplicate reports.

All adverse events/reactions collected for the study will be recorded and summarised in the final study report.

Final v2.0 59 of 63 18 April 2023

The results of the study will be communicated after the end of the study to the investigator and to Competent Authorities/Ethics Committee, as appropriate. They can be submitted to Regulatory Authorities and can be either submitted for publications and/or posted in a publicly available database. The Sponsor reserves the right to review all manuscripts and abstracts before their submission for publication or presentation. This is not intended to restrict or hinder publication or presentation but to allow the sponsor to protect the confidentiality of information and to provide comments that may not yet be available to the investigator. Publications will comply with internal Recordati standards and the International Committee of Medical Journal Editors (ICMJE).

Ownership of all data will remain with the sponsor.

13 APPENDICES

13.1 Appendix 1: List of Supplementary Documents

Number	Title
1	No Objection Letter
2	Sample Case Report Form

# **REVISION HISTORY**

Version No.	Effective Date	Summary of Change(s)
0.5	[12 Dec 2022]	New document
1.0	[12 May 2023]	Update for protocol amendment
2.0	[19 July 2023]	Update for mUFC definition and the requests by OSE
3.0	[ 24 Oct 2023]	Addition of population and analyses
4.0	[ 30 Oct 2023]	Update for exposure data analysis and further clarification of
		on-treatment population

Project Document Version No.: 4.0; Document Effective Date: 30 October 2023

TP-GDO-WW-096-09 Effective Date: 22 Dec 21 Related to: SOP-GDO-WW-019 CONFIDENTIAL

# **LIST OF ABBREVIATIONS**

Abbreviation / Acronym	Definition / Expansion
ACTH	Adrenocorticotropic hormone
AE	Adverse Event
AESI	Adverse Events of Special Interest
BL	Baseline
CD	Cushing's Disease
CRF	Case Report Form
CRH	Corticotropin-releasing hormone
CRO	Contract Research Organisation
CS	Cushing's Syndrome
CT	Computed tomography
DCF	Data Clarification Form
DMP	Data Management Plan
DVS	Data Validation Specification
ECG	Electrocardiogram
eCRF	Electronic Case Report Form
EDC	Electronic Data Capture
EMA	European Medicines Agency
ENCePP	European Network of Centres for Pharmacoepidemiology and Pharmacovigilance
EU	European Union
FSH	Follicle Stimulating Hormone
GPP	Good Pharmacoepidemiology Practices
HbA1C	Glycated Haemoglobin
HCP	Health Care Providers
IEC	Independent Ethics Committee
IRB	Institutional Review Board
ITT	Intention to Treat
LH	Luteinizing Hormone
LTF	Loss to Follow-Up
MedDRA	Medical Dictionary for Regulatory Activities
NOL	No Objection Letter
PT	Preferred Term

Project Document Version No.: 4.0; Document Effective Date: 30 October 2023

# RECORDATI AG, Rare Diseases Branch

LCI699-RECAG-NI-0596 Statistical Analysis Plan

		- · · · · · · · · · · · · · · · · · · ·
Abbreviation / Acronym	Definition / Expansion	
QA	Quality Assurance	
SAP	Statistical Analysis Plan	
SD	Standard Deviation	
SMP	Site Management Plan	
sNDA	Supplemental New Drug Application	
SOC	System Organ Class	
TEAE	Treatment-emergent adverse events	
TFL	Tables, Figures, Listings	
UFC	Urinary free cortisol	
ULN	Upper Limit Normal	
WHO	World Health Organization	
WK	Week	

Project Document Version No.: 4.0; Document Effective Date: 30 October 2023

#### 1 INTRODUCTION

Isturisa® (osilodrostat), an orphan medicine, was approved by the European Union (EU) on 9 January 2020 for endogenous Cushing's Syndrome (CS), and by the United States Food Drug Administration (FDA) on 6 March 2020 for the treatment of Cushing's Disease (CD). Prior to approval and commercialization of osilodrostat in the EU, greater than 50 patients with CS had already been initiated on osilodrostat under the April 2019 French Autorisation Temporaire d'Utilisation (ATU) scheme.

Recordati proposes an FDA label expansion for osilodrostat to include CS. This study therefore intends to evaluate the safety and effectiveness of osilodrostat for the treatment of non-CD CS patients in support of an FDA supplemental New Drug Application (sNDA).

This SAP is based upon the following study documents:

- Study Protocol, Version 2.0 (April 18, 2023)
- Electronic Case Report Design Specification (eCRF), Version 2.0 (January 11, 2023)

#### 2 STUDY OBJECTIVES

The protocol specified study objectives are listed below-

# 2.1 Primary Objective(s)

• To evaluate the effectiveness of osilodrostat in the treatment of non-Cushing's Disease (CD) Cushing's Syndrome (CS)

# 2.2 Secondary Objective(s)

- To assess the long-term effects of osilodrostat in the treatment of non-CD Cushing's Syndrome (CS)
- To assess the change in biochemical variables associated with osilodrostat treatment in non-CD CS patients.
- To assess actual and change in clinical outcomes associated with osilodrostat treatment in non-CD CS patients.
- To characterize initiating doses, up- and down-titration regimens for non-CD CS patients treated with osilodrostat.
- To estimate the incidence of overall treatment-emergent adverse events (TEAEs) and adverse events of special interest (AESI) for non-CD CS patients treated with osilodrostat.

#### 2.3 Exploratory Objective(s)

 To assess change in late night salivary cortisol level from baseline to various timepoints for non-CD CS patients treated with osilodrostat.

Project Document Version No.: 4.0; Document Effective Date: 30 October 2023

CONFIDENTIAL

Page 9 of 31

TP-GDO-WW-096-09 Effective Date: 22 Dec 21

Related to: SOP-GDO-WW-019

[figure not shown]
#### 3 STUDY DESIGN

[figure not shown]
This is a multi-centre, observational, non-comparative, retrospective cohort study designed to evaluate the long-term safety and effectiveness of osilodrostat in non-Cushing's Disease (non-CD) Cushing's

Syndrome (CS) patients. Patients treated with oral osilodrostat regardless of the duration of their treatment will be followed retrospectively for up to 36 months after initiating osilodrostat. Follow-up for each patient will be variable, rather than fixed. Using a variable follow-up, rather than a fixed follow-up period for each patient, maximises the person-time of patient follow-up in the study. This methodological approach allows for increased precision of findings compared to a fixed follow-up period because the unit of observation in analyses is person-time accrued aggregately across all eligible patients, rather than a count denominator of patients exposed to osilodrostat.

Participating institutions will be where the past treatment of patients took place using osilodrostat under Autorisation Temporaire d'Utilisation (ATU) and/or as a part of routine clinical practice. Data will be abstracted from patients' existing electronic, or paper institutional medical records collected during the French ATU and/or routine clinical care. Importantly, the historical decisions of health care providers (HCPs) to treat patients with osilodrostat were made purely at the discretion of the treating physicians as discussed with their patients. Thus, there is no relationship between the decision to treat patients with osilodrostat and inclusion in this study.

The study schematic is presented in Figure 1 below and illustrates the dates corresponding to the study's retrospective follow-up period, the French ATU, the latest date an osilodrostat-treated patient is eligible for inclusion in the cohort study, and general timelines.

\*\*\*at every 12 weeks until the earlier of LFTU, death, or the end of the retrospective follow-up period or treatment discontinuation

Abbreviations: ATU: Autorisation Temporaire d'Utilisation.; F/U: Follow Up; LTFU: Lost to Follow Up,

Clinical practice medical records will be reviewed for all eligible patients who received osilodrostat between April 2019 and the study start date at study sites in France. The study start date was the date the first site was initiated in the study, which was on 16 December 2022. The study will screen all patients at each site who were treated with osilodrostat in France within the frame of the ATU programme prior to commercial availability along with the patients who were treated with commercially available osilodrostat. All patients treated with osilodrostat between April 2019 and the study start date (16 December 2022) will be enrolled in the study. Either the patient has previously signed a general consent for research, or a signed no-

Project Document Version No.: 4.0; Document Effective Date: 30 October 2023

CONFIDENTIAL

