#### **Safety Population**

The Safety population consists of all participants who receive at least one dose of osilodrostat.

Safety analysis will be performed on the Safety population.

Decisions regarding the exclusion of participants and/or participant data from analyses will be made prior to the Database lock (DBL) during the data review meeting and will be documented and approved by Recordati.

The number and percentage of patients included and excluded from each analysis population, along with reasons for exclusion, will be summarized.

A listing of participants included in each analysis population will also be provided. Participants exclusion from analysis sets will be listed with reasons for exclusions.

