#### Reason for Osilodrostat use

- 1) **Short-term use in preparation for surgery**: Patients who took Osilodrostat for < 12 weeks had a surgical procedure to treat Cushing's syndrome and were not restarted on Osilodrostat.
- 2) Chronic use: All other patients

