# 5.9 Safety Analysis

#### 5.9.1 Adverse Events

All AEs, whether they are serious/non-serious, related/unrelated, and all "special situations" reported in participants' charts within the data collection period should be collected. All AEs will be assessed according to incidence, grade, causality, outcome, action taken and seriousness.

TEAE and AESI were defined in section 5.3.3.5

An overview of adverse events will summarize the percentage of participants experiencing deaths, SAEs, AE reported as reason for discontinuation, TEAEs, and AEs possibly related to study drug.

The frequency and percentage of participants with following will be summarized using MedDRA preferred Term nested within SOC.

- TEAE
- TEAE by maximum severity
- TEAEs related to osilodrostat
- TEAE leading to osilodrostat dose interruption/adjustment
- TEAEs leading to study discontinuation
- SAEs including death
- SAEs by maximum severity
- SAEs related to osilodrostat
- Deaths
- AE of Special Interests (AESIs)

Project Document Version No.: 4.0; Document Effective Date: 30 October 2023

CONFIDENTIAL

RECORDATI AG, Rare Diseases Branch LCI699-RECAG-NI-0596

Statistical Analysis Plan

Adverse event summaries will be ordered in terms of decreasing frequency for SOC, and PT within SOC. For incidence counts, each participant will be counted only once within each Preferred Term and within each SOC. Percentages will be based on the number of participants in safety population. For events that are gender-specific, the denominator and computation of the percentage will include only participants from the given gender.

By-participant listings of all adverse events (including non-treatment-emergent events) recorded on the CRF, all TEATs, TEAEs leading to study discontinuation, SAEs including death, and deaths during the treatment period will be presented by participant, visit, preferred term, severity, and relationship to the study drug.

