#### 5.10 Subgroup Analysis

- i) Selected demographics and patient exposure by subgroups
  - (1) Patient disposition
  - (2) Summary of demographic and baseline disease characteristics
  - (3) Concomitant medications
  - (4) Summary of duration of exposure to Osilodrostat
  - (5) Summary of dose change from initial dose by visits
- ii) Selected efficacy endpoints by subgroups
  - (1) Proportion of mUFC response by (week 4 to 60) mITT and On-treatment population
  - (2) Change in mUFC from baseline by visits in mITT and On-treatment population
  - (3) Proportion of salivary cortisol response by (week 4 to 60) mITT and On-treatment population
  - (4) Proportion of composite measures of cortisol level response by (week 4 to 60) mITT and On-treatment population
  - (5) Change in serum cortisol from baseline by visits in mITT and On-treatment population.
- iii) Selected safety endpoints by subgroups
  - (1) Overview of adverse events
  - (2) Summary of adverse events of special interests by system organ class and preferred term

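### The plan claims a person-time unit of observation, but no adverse-event analysis uses person-time or a number at risk, so the incidence percentages depend on the mix of follow-up lengths

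*SAP*

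**What the plan says.** Protocol section 8.1 and SAP section 3 give the same argument for variable follow-up. The SAP states that "the unit of observation in analyses is person-time accrued aggregately across all eligible patients, rather than a count denominator of patients exposed to osilodrostat", and both documents say this increases precision compared with fixed follow-up.

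The spread of follow-up is part of the design. "Patients treated with oral osilodrostat regardless of the duration of their treatment" are included, and they "will be followed retrospectively for up to 36 months after initiating osilodrostat". SAP section 3.3 sets no minimum exposure for safety: "The Safety population consists of all participants who receive at least one dose of osilodrostat".

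One secondary objective (SAP section 2.2) reads "To estimate the incidence of overall treatment-emergent adverse events (TEAEs) and adverse events of special interest (AESI"). Its endpoint (SAP section 3.6.2, item e) is a proportion of participants. SAP section 5.9.1 gives frequencies and percentages, counting each participant once per preferred term and system organ class: "Percentages will be based on the number of participants in safety population".

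SAP section 5.10 iii repeats the adverse-event overview and the "Summary of adverse events of special interests by system organ class and preferred term" by subgroup. One subgroup (SAP section 3.5) is short-term pre-surgical use: "Patients who took Osilodrostat for < 12 weeks had a surgical procedure to treat Cushing's syndrome" and did not restart. The comparison group, labelled chronic use, is everyone else.

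Protocol section 8.7.9 also plans event counts, and TEAE tables through Week 12 and at 12-week intervals after that.

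**The concern.** A proportion of patients with an event has a clear meaning when everyone is observed for the same time. Here a patient treated for a few weeks and one treated for three years each add one to the denominator. The result is not the risk at any defined time. It is an average over whatever follow-up lengths the cohort happens to have.

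Two things are at stake. First, both documents claim a property, person-time with its precision, that the analyses for the incidence objective do not have. Second, the subgroup adverse-event tables set side by side groups that differ in exposure, in one case partly by definition. A reader cannot then tell a difference in tolerability from a difference in time observed. The study is meant to support a supplemental application, so the safety tables will be read closely.

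**Working it through.** **1. Is there a time-based denominator for adverse events anywhere?**

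- SAP section 5.9.1: percentages of safety-population participants only.
- Protocol section 8.7.2: percentages based on the safety or ITT population.
- Protocol section 8.7.9: event counts and 12-week period tables, with no number at risk defined. Under section 8.7.2 the later periods would keep the full denominator after patients have left. SAP section 5.9.1 does not carry these tables forward, and SAP section 5.13 records no decision to drop them.
- SAP section 5.9.5: exposure duration is calculated but is not used as a denominator.
- SAP section 5.3.3.10: Kaplan-Meier with censoring, for time to normalization only.

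So no adverse-event analysis uses person-time or a number at risk. The plan states no adverse-event rate, so there is no figure to reproduce.

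**2. How far can follow-up mix alone move the crude percentage?**

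The assumptions, none of which is a figure for this cohort, are:

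- a constant rate, identical in all patients;
- 100 patients, some followed for 8 weeks and the rest for 156;
- the rate set from two percentages that protocol section 6 reports for the phase III randomised-withdrawal trial in Cushing's disease (28% adrenal insufficiency, 51% hypocortisolism-related events), assumed to be risks by Week 48.

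Formulas, with 52.18 weeks per year:

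- rate = −ln(1 − p) / (48/52.18). For p = 0.28 this is 0.357 per patient-year.
- risk at w weeks = 1 − exp(−rate × w/52.18).
- pooled percentage = share short × risk at 8 weeks + share long × risk at 156 weeks. For example, 0.5 × 5.3% + 0.5 × 65.6% = 35.5%, to rounding.

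| Assumed risk by Week 48 | Rate per patient-year | Risk at 8 / 12 / 156 weeks | Crude % with 20 / 50 / 80% short |
|---|---|---|---|
| 28% | 0.357 | 5.3 / 7.9 / 65.6% | 53.6 / 35.5 / 17.4% |
| 51% | 0.775 | 11.2 / 16.3 / 90.2% | 74.4 / 50.7 / 27.0% |

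The first-event rate is the same in all three mixes of a row. In the 28% row, person-years to first event are 150.0, 99.3 and 48.7, and the rate is 0.357 each time. The exact Poisson 95% intervals are 0.27–0.47, 0.25–0.50 and 0.21–0.57.

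**3. Would one overall rate be enough?**

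Not if events cluster early, as they may during titration. Suppose 30% of patients in each of two groups have an event, spread evenly over the first 8 weeks, with none later.

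- Followed 8 weeks: person-time per patient = 0.7 × 8 + 0.3 × 4 = 6.8 weeks. Rate = 0.3 / (6.8/52.18) = 2.3 per patient-year.
- Followed 156 weeks: 0.7 × 156 + 0.3 × 4 = 110.4 weeks. Rate = 0.3 / (110.4/52.18) = 0.14 per patient-year.

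The risk is identical, yet the rates differ about 16-fold, now in favour of long exposure. Restricting the second group to Weeks 0–12 gives 0.7 × 12 + 0.3 × 4 = 9.6 weeks and a rate of 1.6. The gap shrinks to 9.6/6.8 = 1.4-fold. Rates therefore need to be split by period.

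**4. Can person-time be calculated from what is planned?**

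Mostly. SAP section 5.9.5 reports a high rate of missing end-of-treatment dates and offers approaches A and B. Approach A leaves the date missing for some end-of-study reasons, so A and B do not bracket person-time. The TEAE windows also differ: protocol section 10.1 runs to 30 days after the last dose, while SAP section 5.3.3.11 stops at treatment discontinuation or an earlier end of follow-up. For a 6-week (42-day) course, 30 days adds 30/42 = 71% to time at risk.

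**The case against.** The stated endpoint is a proportion of participants, and the planned tables deliver it. Safety is secondary and descriptive, with no test on adverse events. SAP section 5.10 i(4) shows exposure duration for the same subgroups, so unequal exposure will be visible. Rates could be derived later from the listings. These points stand, and they lower the severity. They do not supply an estimate adjusted for follow-up, and they do not make the person-time sentence true.

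Some stronger readings are tempting but not supported:

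- **That no planned analysis uses time at risk.** Kaplan-Meier time to normalization does. The gap concerns adverse events.
- **That the protocol plans only crude percentages.** It also plans event counts and period tables. What is missing is the number at risk, and their transfer to the SAP.
- **That short-term users will look safer than chronic users.** The short-term group needs under 12 weeks of use, surgery and no restart. Chronic use is all other patients, including those who stopped early for an adverse event, death or another non-surgical reason. Exposure will be unequal, but the direction of the difference in adverse events is not settled.
- **That the illustrated sizes predict this study.** A constant rate is an assumption, and the protocol's own background does not show longer exposure going with higher percentages. Adrenal insufficiency occurred in 7 of 9 patients in the small non-CD study, with median exposure of 12 weeks, against 28% in the longer Cushing's disease trial. The populations differ and nine patients are few.
- **That comparisons with other osilodrostat studies are distorted.** No such comparison of adverse events is planned.

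**Conclusion.** The mismatch is textual and certain. Both documents say that analyses rest on person-time rather than a patient count, and every adverse-event percentage rests on a patient count with no number at risk. The overall incidence figures therefore depend on the follow-up mix, and the subgroup tables compare groups with unequal exposure.

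The size is not known. Under a constant common rate and an 8-week/156-week mix, the same underlying risk gives crude percentages from 17% to 54% (low case) or 27% to 74% (high case). These ranges show the mechanism and are not a forecast. That some follow-up is very short is inferred from the absence of a minimum treatment duration, the one-dose safety population and the SAP's 0-to-4-week exposure class. The actual distribution is not given.

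This should be fixed, but it is not critical: the objective is secondary and descriptive, and the crude percentages remain valid as description.

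**What to change.** Keep the crude percentages. Then:

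1. **Reconcile the TEAE window** between protocol section 10.1 and SAP section 5.3.3.11, and use the same window for time at risk.
2. **In SAP sections 5.9.1 and 5.10 iii, carry forward the protocol's Week 0–12 and later 12-week tables**, with the number at risk at the start of each period, or give cumulative incidence at fixed times. Do this for any TEAE, SAEs, TEAEs leading to discontinuation and each AESI group, overall and by subgroup. Cumulative incidence with censoring is the cleaner choice. With start-of-period denominators, patients leaving at 8 weeks still show 5.3% against 7.9% for a full 12 weeks in the low case.
3. **Add first-event rates per 100 patient-years** with exact Poisson 95% intervals, split by period (for example Weeks 0–12 and after Week 12), not as one constant rate.
4. **Show person-time under approaches A and B**, and state how many patients have no defined end date under A.
5. **Correct the person-time and precision sentence** in protocol section 8.1 and SAP section 3 so that it describes only the analyses that use time at risk, or delete it. Deletion alone removes the false statement but leaves the incidence objective unadjusted for follow-up.

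The cost is SAP wording, one protocol sentence and a few extra tables from data already collected. The drawback is that the rates inherit the imputed end-of-treatment dates.
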